**Table 27. Biomarkers**

	N (%; IC 95%)
ENO1	Yes
	No
	Total
VEGFR2	Yes
	No
	Total
VEGFR3	Yes
	No
	Total
IL8	Yes
	No
	Total
CYP3A4	Yes
	No
	Total
ABCB1	Yes
	No
	Total
POR	Yes
	No
	Total
HIF1- $\alpha$	Yes
	No
	Total
CYP2W1	Yes
	No
	Total
c-Myc	Yes
	No
	Total

### 2.7.2.6 Association between ORR and Biomarkers

In the total analysis population, the association between the marker expression profiles analysed in plasma and treatment response (yes/no) will be assessed using logistic regression models (univariate and multivariate).

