5.4. Sample Size

It is estimated that a total of 43 eligible patients will be enrolled in the study (having received at least one dose of treatment). The design will follow *Simon's two-stage design* for phase II studies, with a baseline number of 18 patients. The combination of TH-302 with sunitinib will be considered as inactive in terms of the response rate if less than 5% of patients are responders, with a response rate threshold of 20%. These figures are based on the results shown with other drugs for the treatment of pNET.

A phase II trial to assess the activity and safety of TH-302 in combination with sunitinib in patients

Should a response be identified in at least 3 out of every 18 patients treated, recruitment will continue up to 43 patients in order to be able to better estimate the response rate. If the study shows a response in at least 8 patients, the treatment is likely to continue its research development.

The likelihood of terminating the study after the first part with 18 patients enrolled is 0.42 if the response rate is 10%, and 0.06 if the response rate is 25%.

The likelihood of not accepting the null hypothesis and considering the combination of TH-302 with sunitinib active with a response rate less than 5% is 5% (Type I or alpha error).

The likelihood of not rejecting the null hypothesis and considering the combination of TH-302 with sunitinib inactive with a response rate greater than 5% is 20% (Type II or beta error). The statistical power of the study will be 0.80.

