### 1.5.4. DETERMINATION OF SAMPLE SIZE

It is estimated that a total of 43 eligible patients will be enrolled in the study (having received at least one dose of treatment). The design will follow Simon's two-stage design for phase II studies, with a baseline number of 18 patients. The combination of TH-302 with sunitinib will be considered as inactive in terms of the response rate if less than 5% of patients are

responders, with a response rate threshold of 20%. These figures are based on the results shown with other drugs for the treatment of pNET.

Should a response be identified in at least 3 out of every 18 patients treated, recruitment will continue up to 43 patients in order to be able to better estimate the response rate. If the study shows a response in at least 8 patients, the treatment is likely to continue its research development.

The likelihood of terminating the study after the first part with 18 patients enrolled is 0.42 if the response rate is 10%, and 0.06 if the response rate is 25%.

The likelihood of not accepting the null hypothesis and considering the combination of TH-302 with sunitinib active with a response rate less than 5% is 5% (Type I or alpha error).

The likelihood of not rejecting the null hypothesis and considering the combination of TH-302 with sunitinib inactive with a response rate greater than 5% is 20% (Type II or beta error). The statistical power of the study will be 0.80.

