**Table 28. Univariate logistic regression**

Variables	Categories	Exp(B)	p-value	95% CI EXP(B)		N
				Inferior	Superior	
ENO1	Yes					
	No					
	Total					
VEGFR2	Yes					
	No					
	Total					
VEGFR3	Yes					
	No					
	Total					
IL8	Yes					
	No					
	Total					
CYP3A4	Yes					
	No					
	Total					
ABCB1	Yes					
	No					
	Total					
POR	Yes					
	No					
	Total					
HIF1- $\alpha$	Yes					
	No					
	Total					
CYP2W1	Yes					
	No					
	Total					
c-Myc	Yes					
	No					
	Total					

In the total analysis population, in the multivariate model, those variables that were found statistically significant ( $p < 0,1$ ), will be entered as factors in the multivariate model for treatment response (yes/no).

Table 29. Multivariate logistic regression

Variables	Categories	Exp(B)	p-value	95% CI EXP(B)		N
				Inferior	Superior	
ENO1	Yes					
	No					
	Total					
VEGFR2	Yes					
	No					
	Total					
VEGFR3	Yes					
	No					
	Total					
IL8	Yes					
	No					
	Total					
CYP3A4	Yes					
	No					
	Total					
ABCB1	Yes					
	No					
	Total					
POR	Yes					
	No					
	Total					
HIF1- $\alpha$	Yes					
	No					
	Total					
CYP2W1	Yes					
	No					
	Total					
c-Myc	Yes					
	No					
	Total					

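### With about 8 responders, SAP 2.7.2.6 has no method for an empty marker-by-response cell and does not name the test behind its p<0.1 entry rule

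*SAP*

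**What the plan says.** SAP 2.7.2.6 relates each marker to response: "treatment response (yes/no) will be assessed using logistic regression models (univariate and multivariate". Table 28 lists ten markers, each coded Yes/No, with columns for Exp(B), p-value, 95% CI and N. The text after it sets the entry rule for Table 29: "those variables that were found statistically significant ( $p < 0,1$ ), will be entered as factors in the multivariate model for treatment response (yes/no".

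On size, SAP 1.5.4 states: "It is estimated that a total of 43 eligible patients will be enrolled in the study". It sets success by the clause "If the study shows a response in at least 8 patients" and gives the activity target in the words "with a response rate threshold of 20" per cent. Protocol 5.4 carries the same rule: "If the study shows a response in at least 8 patients, the treatment is likely to continue its research development". Protocol 5.1 takes blood samples only from patients who consent to the translational sub-study, so fewer than 43 may have data for the blood-sample markers.

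Neither document mentions separation, empty cells, penalised or exact methods, or a minimum cell count. Neither says whether the p-value is Wald, score or likelihood-ratio.

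**The concern.** In a two-by-two table of marker by response, ordinary logistic regression has a finite odds ratio only if all four cells are occupied. With about 8 responders, an uncommon marker can easily leave one empty. The software then prints whatever its iterations had reached: a huge or near-zero Exp(B) with an enormous standard error.

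Two things are at stake. First, Tables 28 and 29 would carry odds ratios and intervals that mean nothing. Second, entry to the multivariate model, and so the model assessed by ROC curve in SAP 2.7.2.9, would depend on an unstated choice of test. This is a failure of the estimator, separate from multiplicity or over-fitting. The prognostic and predictive value of biomarkers is a stated secondary objective (Protocol 1.12, SAP 1.5.5.3).

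**Working it through.** The SAP gives no figure for the marker models. The planning figure that enters is the number of responders. The power of 0.80 stated beside it does not reproduce at 5% against 20%: continuing at 3 or more of 18 and succeeding at 8 or more of 43 gives 0.56, with alpha 0.0009. At 10% against 25% it gives 0.800 and 0.048. That is a separate matter; here it only motivates a check at 11 responders.

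**Inputs**
- N = 43 at most (SAP 1.5.4).
- R = 8 responders, M = 43 − 8 = 35 non-responders. Expected responders at 20%: 0.20 × 43 = 8.6. Check at R = 11 (0.25 × 43 = 10.75).
- Marker prevalence q: not in the documents. Assumed 5% to 50%; values above 50% mirror these.
- Markers independent of response and of each other: assumed in step 3.

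**Step 1. What one empty cell does.** Take 8 responders among 20 marker-positive patients and 0 among 23 marker-negative.
- Maximum-likelihood odds ratio: (8 × 23)/(12 × 0), infinite. Newton-Raphson stopped after 20 steps gives b = 20.8, SE = 8381, so z = 0.0025, Wald p = 0.998 and Exp(B) about 1e9. The printed values depend on where the iterations stop.
- Likelihood ratio from the same model: 2 × [8 ln(8/20) + 12 ln(12/20) − 8 ln(8/43) − 35 ln(35/43)] = 2 × (−13.460 + 20.659) = 14.40 on 1 df, p = 0.00015.
- Fisher: C(20,8)/C(43,8) = 125,970/145,008,513 = 0.0009.
- Firth, which for one binary marker equals adding 0.5 to each cell: (8.5 × 23.5)/(12.5 × 0.5) = 32.0, penalised likelihood-ratio p = 0.0006.

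**Step 2. Ranking under Wald.** With 8/8 responders and 10/35 non-responders positive, Wald p = 0.999 (likelihood ratio 4.6e-5, Fisher 0.0003, Firth 0.0002). With the weaker pattern 7/8 and 10/35, Wald p = 0.012. The weaker marker passes p<0.1 and the stronger one fails.

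**Step 3. How often a cell is empty.** For an unassociated marker,

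P = 1 − [1 − (1−q)^R − q^R] × [1 − (1−q)^M − q^M].

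At q = 0.2: 0.8^8 = 0.1678 and 0.8^35 = 0.0004, so P = 1 − 0.8322 × 0.9996 = 0.168.

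| Prevalence | 8 of 43 respond | 11 of 43 | 6 of 30 (assumed) |
|---|---|---|---|
| 5% | 72% | | |
| 10% | 45% (0.445) | 34% | 57% |
| 20% | 17% | 9% | 27% |
| 30% | 6% | 2% | 12% |
| 40% | 1.7% | | |
| 50% | 0.8% | | |

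For ten markers, two each at 10%, 20%, 30%, 40% and 50%, the chance of at least one empty cell is 1 − (0.555 × 0.832 × 0.942 × 0.9825 × 0.992)² = 0.82. A three-marker multivariate model is separated in about 45%, 15%, 5% and 2% of simulated data sets at 20%, 30%, 40% and 50% prevalence (600 per setting).

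**Step 4. Is a marker wrongly lost in the frequent cases?** The chance that K carriers include no responder is C(43−K,8)/C(43,8).

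| Carriers | Chance | Firth p | Fisher p |
|---|---|---|---|
| 2 | 66% | 0.88 | 1.0 |
| 4 | 42% | 0.52 | 1.0 |
| 6 | 27% | 0.31 | 0.57 |
| 9 | 13% | 0.13 | 0.17 |

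None passes p<0.1 under a sound method, so failing the screen is no error there; the printed odds ratio and interval are the harm. The unstated test can also err the other way. For 0/9 against 8/34 the likelihood ratio is 2 × [8 ln(8/34) + 26 ln(26/34) + 20.659] = 2 × (−18.550 + 20.659) = 4.22, p = 0.040. That marker would enter under the likelihood-ratio test and not under Firth.

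**The case against.** The strongest reply is that nothing in the SAP says Wald. A reader might infer that perfectly separating markers will be dropped. The Exp(B), p-value and CI layout is typical of Wald output, but that is inference. The likelihood-ratio p from the same model keeps the 8/20 against 0/23 marker. This stands, so the loss of a strong marker must be stated conditionally. It does not rescue the odds ratio or its Wald interval, which are unusable whichever test is used.

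A reader might also infer that empty cells will be common across the panel. The documents give no marker frequencies or cut-offs. VEGFR2 and ABCB1 each cover several variants (SAP 2.7.2.5), and if Yes means any variant, prevalence rises and empty cells become rarer. The coding is unstated, so this stands too.

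A third inference joins the two: that strong markers will commonly be lost. Step 4 does not support it. The frequent empty cells come from uncommon markers that fail the screen under Firth as well. For the balanced example, 0/23 has probability 0.0009 without association. A truly strong balanced marker would produce an empty cell more often, but the documents give no effect size from which to compute how often.

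Finally, 8 responders is the threshold for success, not a forecast. The entry rule governs only the multivariate model: Table 28 still shows every marker, and the PFS and OS models use them as well. These points limit the consequence without closing the gap.

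**Conclusion.** The point holds in a limited form. SAP 2.7.2.6 specifies ordinary logistic regression for a data set in which an empty cell is a realistic outcome, and it leaves open both the handling of that cell and the test that drives selection. That the odds ratio and Wald CI then have no meaning is certain. That a strong marker fails the p<0.1 rule is certain only if Wald p-values are used.

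Frequency depends on assumed prevalence. With 8/43 responders and no association, it runs from about 45% per marker at 10% to under 2% at 40-50%, and is about 82% for at least one of ten independent markers spread over 10-50%. It falls with more responders and rises if fewer patients have marker data. In most low-prevalence cases the harm is an uninterpretable estimate, not a wrong exclusion.

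This affects a secondary objective and leaves the response-rate decision untouched. It should be corrected because the remedy is cheap and must be fixed before the data are seen.

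**What to change.** In SAP 2.7.2.6, state that Tables 28 and 29 are fitted by Firth penalised logistic regression, with profile penalised-likelihood confidence intervals and p-values, and that this p-value is the one used for the p<0.1 entry rule. Exact logistic regression, or Fisher's exact test for single binary markers, would also be acceptable for the p-value. Switching to likelihood-ratio p-values alone would stop strong separated markers being lost but would leave the odds ratios infinite. Adding responder counts by marker group to Table 28 would let a reader see any empty cell.

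The cost is SAP wording and a standard software option, with no change to data collection. Firth estimates are shrunk slightly towards no effect, and intervals for sparse markers will be finite but wide, which reflects how little such tables can say.

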**Table 28. Univariate logistic regression**

Variables	Categories	Exp(B)	p-value	95% CI EXP(B)		N
				Inferior	Superior	
ENO1	Yes					
	No					
	Total					
VEGFR2	Yes					
	No					
	Total					
VEGFR3	Yes					
	No					
	Total					
IL8	Yes					
	No					
	Total					
CYP3A4	Yes					
	No					
	Total					
ABCB1	Yes					
	No					
	Total					
POR	Yes					
	No					
	Total					
HIF1- $\alpha$	Yes					
	No					
	Total					
CYP2W1	Yes					
	No					
	Total					
c-Myc	Yes					
	No					
	Total					

In the total analysis population, in the multivariate model, those variables that were found statistically significant ( $p < 0,1$ ), will be entered as factors in the multivariate model for treatment response (yes/no).

Table 29. Multivariate logistic regression

Variables	Categories	Exp(B)	p-value	95% CI EXP(B)		N
				Inferior	Superior	
ENO1	Yes					
	No					
	Total					
VEGFR2	Yes					
	No					
	Total					
VEGFR3	Yes					
	No					
	Total					
IL8	Yes					
	No					
	Total					
CYP3A4	Yes					
	No					
	Total					
ABCB1	Yes					
	No					
	Total					
POR	Yes					
	No					
	Total					
HIF1- $\alpha$	Yes					
	No					
	Total					
CYP2W1	Yes					
	No					
	Total					
c-Myc	Yes					
	No					
	Total					

### 2.7.2.7 Association between PFS and Biomarkers

In the total analysis population, the association between the marker expression profiles analysed in plasma and PFS will be assessed using the Cox regression models (univariate and multivariate).

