1.12 Primary and Secondary Objectives

The main purpose of the study is to determine the safety and activity of TH-302 in combination with sunitinib in patients with a well- or moderately-differentiated metastatic pancreatic neuroendocrine tumour (pNET). Drug activity will be measured according to the objective response rate (ORR), as measured by RECIST criteria version 1.1, with assessments performed every 8 weeks, regardless of delays due to adverse events. ORR is defined as the percentage of patients with confirmed complete response (CR) or confirmed partial response (PR) according to RECIST criteria v1.1, relative to the total analysis population. Confirmed responses are those that persist in a repeat imaging study conducted ≥ 4 weeks after initial documentation of response.

The secondary objectives of the study are:

- Progression-free survival
- Time to tumour progression
- Duration of response
- Overall survival
- Safety of TH-302 treatment in combination with sunitinib.
- Prognostic/predictive value of biomarkers analysed in peripheral blood and in paraffin-embedded tumour tissue.

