9. STATISTICAL ANALYSIS

9.1. *Descriptive Analysis*

The descriptive analysis of patient characteristics will include demographic data, disease-specific data and prior treatments. Qualitative data will be described with absolute frequencies and corresponding percentages. Quantitative data will be studied using the mean \pm standard deviation, median, minimum and maximum values. The response percentages will be estimated using confidence intervals of 95%. In the safety analysis, adverse events will be specified according to the maximum grade described at the discretion of the investigator and defined by NCI-CTCAE, version 4.0 (see section 10.2.3.), including adverse events described from treatment initiation until 28 days following its completion.

The following safety analysis data will be presented:

- Temporary and permanent treatment discontinuations due to an adverse event.
- Deaths.
- Adverse Events (AEs) and Serious Adverse Events (SAEs).
- Hospitalisations.
- Use of concomitant medication and growth factors.

9.2. *Inferential Analysis*

The objective response rate corresponding to the percentage of patients in which there is confirmation of a complete response (CR) or a partial response (PR) according to RECIST criteria, in relation to the total analysis population, will include a confidence interval of 95%. The association between the marker expression profiles analysed in plasma and in tumour tissue for treatment response (yes/no) will be assessed using logistic regression models and univariate and multivariate Cox regression, establishing the corresponding *hazard ratio* and confidence interval at 95%. The predictive value (of genetic biomarkers, in plasma and tumour tissue) of each model will be estimated using an area under the ROC curve.

The survival analyses will be performed using the Kaplan-Meier method presented with the corresponding graph, as well as by Cox regression analysis to obtain the *hazard ratios* and confidence intervals for the associations. For patients without documented progression or death at the time of analysis, the PFS will be censored at the last date of tumour assessment. For patients who have not died at the time of analysis, the OS will be censored.

All statistical tests are bilateral, two-tailed tests, and all values with $p < 0.05$ will be considered significant.

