#### 1.4.1.1 Inclusion criteria

For inclusion in the study subjects should fulfil the following criteria:

1. Age  $\geq$  18 years capable of giving informed consent.
2. ECOG performance status (Eastern Cooperative Oncology Group) 0 or 1
3. Pancreatic neuroendocrine tumours (pNET) diagnosed histologically with a Ki67  $\leq$  20% (well- or moderately-differentiated tumours).
4. Evidence of unresectable or metastatic disease. Locally advanced disease must not be amendable to surgical resection or radiation therapy with curative intent.
5. Prior systemic therapy is not permitted. Patients may be treated with somatostatin analogues prior to or during the trial. Concomitant or prior interferon (IFN) treatment is not permitted.
6. Tumour progression documented by CT scan, MRI or octreoscan within 12 months prior to the baseline visit.

7. Measurable disease by RECIST 1.1 criteria. Measurable lesions that have been previously radiated will not be considered target lesions unless increase in size has been observed following completion of radiation therapy.
8. The patient must be able to consume the medication orally.
9. Life expectancy more than 12 weeks.
10. The required laboratory values corresponding to adequate organ function and bone marrow are as follows.
  - Aspartate aminotransferase (AST) and alanine aminotransferase (ALT)  $\leq 2.5 \times$  upper limit of normal (ULN), or AST and ALT  $\leq 5 \times$  ULN if liver function abnormalities are secondary to underlying malignancy.
  - Total serum bilirubin  $\leq 1.5 \times$  ULN
  - Serum albumin  $\geq 3.0$  g/dl
  - Absolute neutrophil count  $\geq 1500/\mu\text{l}$ .
  - Platelets  $\geq 100,000/\mu\text{l}$
  - Haemoglobin  $\geq 5.6$  mmol/l (9 g/dl)
  - Creatinine clearance  $> 40$  ml/min (Cockcroft and Gault Formula)
11. Suitable cardiac function:
  - 12-lead ECG with no pathological findings (non-clinically significant abnormalities are permitted)
  - Normal echocardiogram/MUGA normal (LVEF  $\geq 50\%$ )
12. Informed consent with date and signature indicating that the patient (or legal representative) has been informed of all study aspects prior to enrolment.
13. The patient must be able to comply with the required study visits, treatment, laboratory tests and other study procedures.

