## 1.5. STATISTICAL METHODS AND SAMPLE SIZE DETERMINATION

### 1.5.1. DESCRIPTION OF ANALYSIS SETS

#### 1.5.1.1 Total analysis population

All safety and efficacy analyses will be based in the total analysis population. Any patient fulfilling all the inclusion criteria and none of the exclusion criteria will be included the total analysis population.

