**Table 30. Univariate Cox regression PFS**

Variables	Categories	HR	p-value	95% CI HR		N
				Inferior	Superior	
ENO1	Yes					
	No					
	Total					
VEGFR2	Yes					
	No					
	Total					
VEGFR3	Yes					
	No					
	Total					
IL8	Yes					
	No					
	Total					
CYP3A4	Yes					
	No					
	Total					
ABCB1	Yes					
	No					
	Total					
POR	Yes					
	No					
	Total					
HIF1- $\alpha$	Yes					
	No					
	Total					
CYP2W1	Yes					
	No					
	Total					
c-Myc	Yes					
	No					
	Total					

In the total analysis population, in the multivariate model, those variables that were found statistically significant ( $p < 0,1$ ), will be entered as factors in the multivariate model for PFS.

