### 2.7.2.8 Association between OS and Biomarkers

In the total analysis population, the association between the marker expression profiles analysed in plasma and OS will be assessed using the Cox regression models (univariate and multivariate).

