**Table 32. Univariate Cox regression OS**

Variables	Categories	HR	p-value	95% CI HR		N
				Inferior	Superior	
ENO1	Yes					
	No					
	Total					
VEGFR2	Yes					
	No					
	Total					
VEGFR3	Yes					
	No					
	Total					
IL8	Yes					
	No					
	Total					
CYP3A4	Yes					
	No					
	Total					
ABCB1	Yes					
	No					
	Total					
POR	Yes					
	No					
	Total					
HIF1- $\alpha$	Yes					
	No					
	Total					
CYP2W1	Yes					
	No					
	Total					
c-Myc	Yes					
	No					
	Total					

In the total analysis population, in the multivariate model, those variables that were found statistically significant ( $p < 0,1$ ), will be entered as factors in the multivariate model for OS.

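### The PFS and OS biomarker Cox models leave out Ki-67, which is known for every analysed patient, so a tissue or plasma marker that tracks tumour grade may look prognostic without adding to grade

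*SAP*

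**What the plan says.** The objective is given in Protocol 1.12 as "Prognostic/predictive value of biomarkers analysed in peripheral blood and in paraffin-embedded tumour tissue". SAP 1.5.5.3 carries it over as a secondary efficacy objective.

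For PFS, SAP 2.7.2.7 plans that the association between "marker expression profiles analysed in plasma and PFS will be assessed using the Cox regression models (univariate and multivariate"). SAP 2.7.2.8 plans the same for "marker expression profiles analysed in plasma and OS will be assessed using the Cox regression models (univariate and multivariate"). Although the text says plasma, Tables 30 to 33 list ten rows of mixed origin: ENO1, VEGFR2, VEGFR3, IL8, CYP3A4, ABCB1, POR, HIF1-alpha, CYP2W1 and c-Myc. Markers with univariate p<0.1 "will be entered as factors in the multivariate model for PFS", and likewise "will be entered as factors in the multivariate model for OS". Tables 31 and 33 are titled as logistic regression but have hazard-ratio columns, so I read them as Cox models.

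No clinical covariate is named in those sections, in SAP 1.5.5.3 or in SAP 2.7.2. Protocol 9.2 speaks only of "univariate and multivariate Cox regression, establishing the corresponding" hazard ratios and intervals. In this plan, multivariate means biomarkers adjusted for other biomarkers.

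Ki-67 is available. Inclusion criterion 3 requires "Pancreatic neuroendocrine tumours (pNET) diagnosed histologically with a Ki67" of at most 20%. SAP 1.5.1.1 adds: "Any patient fulfilling all the inclusion criteria and none of the exclusion criteria will be included the total analysis population". SAP Table 7 tabulates Ki-67 in four bands with no unknown row, whereas histological grade has one. Protocol Annex 2 uses Ki-67, with mitotic count, to separate G1 from G2.

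**The concern.** A prognostic marker is useful to the extent that it tells the clinician something the pathology report does not. Protocol 3.5 hopes that the hypoxia proteins will supply information fit for clinical practice. If one of them is simply more often positive in G2 than in G1 tumours, and G2 tumours progress sooner, its hazard ratio will differ from 1 through grade alone. The planned models cannot separate that from an effect of the marker itself. The p<0.1 screen does not help, because grade is absent from the multi-marker model too.

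At stake is the interpretation of a secondary objective. The primary response analysis is untouched.

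**Working it through.** **The plan's own figure.** The documents give no event count or power for the biomarker models. The only sizing statement is the two-stage response design (18, then 43 patients, 5% against 20%, alpha 5%, power 0.80). Its rule (at least 3 of 18, then at least 8 of 43) gives alpha 0.0009 and power 0.56 at those rates, so it does not reproduce. That is a separate matter; only N = 43 is used here.

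**Inputs from the documents**
- N = 43, assuming the trial runs to its second stage.
- Accrual 24 months, follow-up 20 months (Protocol 1.16).
- Median PFS on sunitinib 11.4 months and one-year survival 81.1% (Protocol 3.3, SAP 1.1.1).
- Two-sided 0.05 (SAP 1.5.5.3).

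**Assumed, because the documents are silent**
- 60% of patients are G2.
- Hazard ratio of G2 to G1: 1.5, 2 or 3.
- Marker positive in G1/G2: 40/40% (no link), 30/60% or 20/80%.
- The marker has no effect of its own.
- Grade stands in for Ki-67 as a two-level variable.

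**Expected events.** With exponential times and uniform accrual, events = 43 × [1 − (e^(−20λ) − e^(−44λ)) / (24λ)].
- PFS: λ = ln 2 / 11.4 = 0.0608. Events = 43 × [1 − (0.2964 − 0.0689) / 1.459] = 43 × 0.844 = 36. Medians of 9 to 20 months give 39 to 28.
- OS: λ = −ln(0.811) / 12 = 0.01746, median 39.7 months. Events = 43 × [1 − (0.7053 − 0.4639) / 0.4190] = 43 × 0.424 = 18. Medians of 30 to 60 months give 22 to 13.

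**Expected bias, by hand.** For a marker acting only through grade, ln HR(marker) ≈ [P(G2 | positive) − P(G2 | negative)] × ln HR(grade).
- 30/60%: P(G2 | positive) = 0.36/0.48 = 0.750 and P(G2 | negative) = 0.24/0.52 = 0.462, difference 0.288. For grade HRs of 1.5, 2 and 3 the marker HR is about 1.12, 1.22 and 1.37.
- 20/80%: 0.48/0.56 = 0.857 and 0.12/0.44 = 0.273, difference 0.584. The marker HR is about 1.27, 1.50 and 1.90.

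**Simulation.** There were 2,500 trials of 43 patients per setting, with exponential times, censoring uniform on 20 to 44 months, and a Cox Wald test of the marker without and with grade. Trials with fewer than three patients in any marker or grade group were dropped. The entries are the share with p<0.05 unadjusted / adjusted, then the median unadjusted marker HR.

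| Grade HR | G1/G2 positivity | PFS p<0.05 | PFS HR | OS p<0.05 | OS HR |
|---|---|---|---|---|---|
| 1.5 | 40/40% | 0.055 / 0.062 | 1.00 | 0.042 / 0.044 | 0.99 |
| 1.5 | 30/60% | 0.060 / 0.052 | 1.13 | 0.046 / 0.045 | 1.12 |
| 1.5 | 20/80% | 0.097 / 0.056 | 1.27 | 0.052 / 0.059 | 1.30 |
| 2 | 40/40% | 0.054 / 0.063 | 1.02 | 0.045 / 0.054 | 1.01 |
| 2 | 30/60% | 0.100 / 0.059 | 1.23 | 0.060 / 0.053 | 1.22 |
| 2 | 20/80% | 0.197 / 0.059 | 1.48 | 0.102 / 0.050 | 1.50 |
| 3 | 40/40% | 0.046 / 0.053 | 1.01 | 0.041 / 0.053 | 1.01 |
| 3 | 30/60% | 0.144 / 0.055 | 1.35 | 0.081 / 0.053 | 1.34 |
| 3 | 20/80% | 0.396 / 0.057 | 1.85 | 0.194 / 0.066 | 1.85 |

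The simulated hazard ratios agree with the hand calculation. With grade in the model, the median marker HR in the linked settings is 0.97 to 1.03. Simulation error is about 0.4 percentage points near 5% and 1 point near 40%. In the linked settings the unadjusted marker passes the p<0.1 entry screen in 12-52% of PFS and 10-32% of OS analyses.

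**The case against.** Four points on the other side carry weight.

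- **The plan estimates associations, not independent effects.** A marker that tracks grade really is associated with PFS, so rejecting the hypothesis of no marginal association is not an error of the test as written. This stands as a matter of wording, and the figures above should be read as the risk of crediting a marker with something grade already supplies. It does not remove the gap, because a marker meant to inform practice has to add to a grade already known.
- **The size is assumed.** The documents give no Ki-67 hazard ratio within the eligible range and do not say that any listed marker correlates with grade. A reader might infer that a grade-tracking marker will be reported as prognostic, or that the error rate exceeds 5% in general. Neither is supported. Even in the strongest setting the marker is flagged in 40% of PFS and 19% of OS analyses, and without a link the rate stays at 4-6%.
- **Most rows are not exposed.** A reader might take all ten rows to be affected. Six of them (VEGFR2, VEGFR3, IL8, CYP3A4, ABCB1, POR) are listed in SAP 1.5.2 as polymorphisms, and Protocol 8.1 genotypes them from peripheral-blood DNA. Genotype is fixed before the tumour, so the mechanism hardly applies. This stands and narrows the point to four markers.
- **Other problems are firmer.** Ten independent tests at 0.05 give 1 − 0.95^10 = 40% chance of at least one false positive per endpoint, with no assumption about grade. That is true, but it is a separate issue and does not answer this one.

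**Conclusion.** The specification gap holds on the documents alone: the PFS and OS models contain only biomarkers, Ki-67 is known for every analysed patient, and as planned the hazard ratios cannot show whether ENO1, HIF1-alpha, CYP2W1 or c-Myc adds to grade. Such a marker may appear prognostic without doing so.

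The size is conditional. For grade hazard ratios of 1.5 to 3, a marker with no effect of its own reaches p<0.05 in 6-14% (30/60% link) or 10-40% (20/80% link) of PFS analyses, and in 5-8% or 5-19% of OS analyses. Adjustment brings this to 5-7%. Without a link, adjusting makes no material difference.

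It would go too far to ask for Ki-67 in every model. With about 18 deaths, OS supports roughly one marker plus Ki-67 at a time, and the response models rest on few responders (8 is the threshold for further development). This is a worthwhile, inexpensive improvement to a secondary analysis.

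**What to change.** In SAP 2.7.2.7 and 2.7.2.8, for ENO1, HIF1-alpha, CYP2W1 and c-Myc only:

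- Add to each single-marker Cox model (Tables 30 and 32) a second version that includes baseline Ki-67. Enter it as a continuous term if the numeric value is captured. The documents show only the four bands of Table 7, so this needs checking. Otherwise use G1/G2, which the Ki-67 bands can supply (at most 2% against above 2%) where histological grade is recorded as unknown.
- Report the marker hazard ratio with its 95% interval both without and with Ki-67.
- State that any claim of independent prognostic value rests on the adjusted hazard ratio and that the unadjusted one is descriptive.

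This is not required for the germline polymorphisms, the response models or the multi-marker OS model.

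The cost is SAP wording and one degree of freedom per adjusted model. No new visits or samples are needed. The one check is whether the database holds Ki-67 as a number.
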